- Number and percentage of blastocysts surviving cryopreservation and number and percentage of blastocysts with re-expansion after cryopreservation
- Number of cryopreserved cycles initiated within 12 months from the start of controlled ovarian stimulation, and number and percentage of cryopreserved cycles with blastocyst transfer
- Circulating concentrations of AMH, FSH, LH, estradiol, progesterone, inhibin A and inhibin B on stimulation day 5, end-of-stimulation and oocyte retrieval, and FSH population pharmacokinetic parameters
- Total gonadotropin dose, number of stimulation days and number of dose adjustments

Date: 25 Apr 2018 E-Study Protocol-22377; Ver. 1.0 Supersedes: None Page 5 of 159

- Frequency and intensity of adverse events
- Changes in circulating levels of clinical chemistry and hematology parameters and proportion of subjects with markedly abnormal changes
- Frequency and intensity of injection site reactions (redness, pain, itching, swelling and bruising) assessed by the subject during the stimulation period
- Proportion of subjects with treatment-induced anti-FSH antibodies, overall as well as with neutralizing capacity
- Frequency and intensity of immune-related adverse events
- Proportion of subjects with cycle cancellations due to an adverse event, including immunerelated adverse events, or due to technical malfunctions of the administration pen
- Proportion of subjects with OHSS, overall and by grade, and proportion of subjects with moderate/severe OHSS
- Proportion of subjects hospitalized due to OHSS and proportion of subjects undergoing paracentesis due to OHSS
- Rate of multi-fetal gestation, biochemical pregnancy, spontaneous abortion, ectopic pregnancy (with and without medical/surgical intervention) and vanishing twins in the fresh cycle and in the cryopreserved cycles
- Technical malfunctions of the administration pen

POST-TRIAL INFORMATION

Post-trial Objectives

- To establish the efficacy of controlled ovarian stimulation with FE 999049 with respect to live birth rates based on the fresh cycle and/or cryopreserved cycles
- To characterize the neonatal health associated with controlled ovarian stimulation with FE 999049, including minor/major congenital anomalies at birth, 4 weeks and 1 year after birth in the fresh cycle and cryopreserved cycles

Post-trial Endpoints

- Cumulative live birth rate after the fresh cycle and cryopreserved cycles initiated within 12 months from the start of controlled ovarian stimulation

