5.4 Conditions for Storage and Use

The investigator will ensure that the medicinal products will be stored in appropriate conditions in a secure location with controlled access. The storage compartment shall be monitored regularly and the temperature shall be documented. Deviations in storage temperature must be reported to Ferring as instructed in the IMP/NIMP handling guideline.

The storage conditions for the IMPs and NIMPs will be as described in the trial-specific or commercial box labelling.

Information on how to administer the medicinal products will be provided in Instructions for Use prepared for the IMPs and in the Package Inserts for the NIMPs.

Trial Code: 000002 Date: 25 Apr 2018 E-Study Protocol-22377; Ver. 1.0

> Supersedes: None Page 65 of 159

In case of technical malfunction of an administration pen, all relevant details (including time, date, a description of the malfunction and whether dosing was affected) of the incidence should be reported, the pen should be replaced and the treatment continued.

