6.1.5 End-of-stimulation

The end-of-stimulation visit will take place when the subject reaches the criterion for triggering of final follicular maturation or if the cycle is canceled. Administration of hCG or GnRH agonist must take place the same day as the criterion for triggering of final follicular maturation, i.e. ≥ 2 follicles with a diameter of ≥ 17 mm, is met. Administration of FE 999049 or placebo after reaching the triggering criterion is not allowed.

Criterion for triggering of final follicular maturation with 10,000 IU hCG:

• <20 follicles with a diameter of \geq 12 mm

Date: 25 Apr 2018 E-Study Protocol-22377; Ver. 1.0 Supersedes: None Page 75 of 159

Criterion for triggering of final follicular maturation with 4 mg GnRH agonist:

• ≥20 follicles with a diameter of ≥12 mm or serum estradiol concentration ≥3,000 pg/mL (local laboratory)

If after 8 days of stimulation, the investigator judges that the triggering criterion, i.e. ≥ 2 follicles with a diameter of ≥ 17 mm, is not likely to be reached by day 20, the cycle will be canceled. If the triggering criterion is not met after 20 days of stimulation, the cycle will be canceled.

The investigator also has the option of canceling the cycle for other relevant medical reasons, including adverse events and technical malfunctions of the administration pen. In the latter event, the option of replacing the administration pen and continuing treatment should be considered.

The following must take place at end-of-stimulation visit:

- Transvaginal ultrasound of uterus (endometrial thickness, echogenicity pattern) and ovaries (number and size of follicles, ovarian volume)
- Blood collection for central laboratory analysis of:
 - clinical chemistry and hematology parameters
 - endocrine parameters (AMH, FSH, LH, estradiol, progesterone, inhibin A and inhibin B) –
 the blood sample must be drawn at least 8 hours after the latest administration of IMP and GnRH antagonist
- Blood collection for local laboratory analysis of estradiol (used to determine the triggering drug)
- Dispensing of hCG or GnRH agonist, as applicable
- Collection of local tolerability data (diary pages)
- Drug accountability of IMP and GnRH antagonist
- Recording of use of any concomitant medication
- Recording of adverse events

For subjects who receive a triggering drug, the next visit is the oocyte retrieval visit which must be scheduled $36h (\pm 2h)$ after the administration of hCG or GnRH agonist.

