7.2.10 Technical Malfunctions of the Administration Pen

In case of technical malfunction of an administration pen that results in a replacement of the pen, all relevant details (including time, date, a description of the malfunction and whether dosing was affected) of the incidence should be reported in the eCRF, the pen should be replaced and the treatment continued. Human errors such as misunderstanding of instructions or incorrect handling of the device should not be regarded as technical malfunctions.

In case of adverse events caused by malfunction of the administration pen, these will be identified and described.

Date: 25 Apr 2018 E-Study Protocol-22377; Ver. 1.0 Supersedes: None Page 104 of 159

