10.11 Pen Malfunction

The frequency of reported malfunctions of the administration pen will be presented in a summary table. For confirmed pen malfunctions, the categories include: not able to detach the pen cap, not able to click / screw-on the needle due to damaged thread on cartridge holder, not able to dial the dose, not able to inject the dose, and other.

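### Protocol 7.2.10 limits eCRF reporting of pen malfunctions to those with a pen replacement, so a malfunction that ends in cancellation without a new pen can be missing from the malfunction table

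*Protocol*

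**What the plan says.** The endpoint lists in the Protocol (Synopsis and section 2.2) and in SAP 2.2 carry two pen items. One is the occurrence of technical malfunctions. The other is "Proportion of subjects with cycle cancellations due to an adverse event, including immunerelated adverse events, or due to technical malfunctions of the administration pen".

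Three Protocol sections say what happens when a pen fails:

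- Section 5.4 sets no condition on which failures are reported: "In case of technical malfunction of an administration pen, all relevant details (including time, date, a description of the malfunction and whether dosing was affected". It adds that these details "of the incidence should be reported, the pen should be replaced and the treatment continued". It does not say where the report goes.
- Section 7.2.10 is the assessment section for the malfunction endpoint. It opens "In case of technical malfunction of an administration pen that results in a replacement of the pen, all relevant details", sends the report to the eCRF, and gives the same replace-and-continue instruction.
- Section 6.1.5 adds another route: "The investigator also has the option of canceling the cycle for other relevant medical reasons, including adverse events and technical malfunctions of the administration pen". For a pen failure, replacing the pen and going on is only to be considered.

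On the analysis side, Protocol 9.8.2.10 tabulates technical malfunctions. SAP 10.11 states: "The frequency of reported malfunctions of the administration pen will be presented in a summary table". Cancellations are handled separately: Protocol 7.2.6 records the reason for each one, and Protocol 9.8.2.6 and SAP 10.7 tabulate them by reason.

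**The concern.** Two sections set the reporting scope for one endpoint, and they differ. The case on which they differ is one the Protocol itself foresees: the pen fails, the investigator cancels, and no new pen is issued. Section 5.4 asks for a report of that failure; section 7.2.10 does not.

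Nothing says which section governs. A site or eCRF designer who follows 7.2.10 to the letter would leave the event out, while one who follows 5.4 would include it. The count could then depend on which section was read. The malfunction table could also show fewer events than the cancellation table attributes to the pen. The affected cases are those in which a device failure cost the woman her cycle, so a reader of the device results would want them in the count.

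**Working it through.** No arithmetic applies, because the plan states no malfunction or cancellation rate for the pen. The check sets the rules side by side for the three outcomes that the Protocol allows after a malfunction.

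| Outcome | Report asked for by 5.4 | Report asked for by 7.2.10 (eCRF) | Shown as a cancellation reason (SAP 10.7) |
|---|---|---|---|
| A. Pen replaced, treatment continued | yes | yes | no |
| B. Pen replaced, cycle later canceled for the malfunction | yes | yes | yes |
| C. Cycle canceled, no new pen | yes | no | yes |

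1. Rows A and B raise no difficulty, since both sections ask for a report.

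2. Row C is permitted by 6.1.5, where replacement is something to consider and not a condition. It is the only row on which 5.4 and 7.2.10 disagree.

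3. The analysis text does not settle row C. Neither Protocol 9.8.2.10 nor SAP 10.11 carries a replacement condition, but a table of reported malfunctions can hold only what was reported. Row C is counted if sites worked to 5.4 and can be missing if they worked to 7.2.10.

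4. The cancellation record is not a substitute. Protocol 7.2.6 asks for a reason. It does not ask when the malfunction happened, what went wrong or whether a dose was affected, all of which 5.4 and 7.2.10 collect. SAP 10.11 needs the description, because it sorts confirmed malfunctions by type, such as failure to dial or to inject the dose.

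5. The undercount can be bounded but not estimated. Let c be the number of row C events. If 5.4 was followed throughout, none is lost; if 7.2.10 was followed throughout, c are lost. Assuming one malfunction per canceled cycle, c cannot exceed the number of cancellations that SAP 10.7 attributes to the pen. The documents give no value for that number, and it may be zero.

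**The case against.** The strongest defense is that 5.4 already asks for every malfunction, and neither counting rule is limited to replaced pens. Read together, 5.4, Protocol 9.8.2.10 and SAP 10.11 report and count a canceling malfunction. A reader might infer from 7.2.10 alone that canceling malfunctions are always excluded from the count. The documents do not support that: 5.4 can be read to include them, and a malfunction followed by a replaced pen and then a cancellation meets 7.2.10 as well. What remains is that 5.4 sits under storage and use and names no destination for the report, while 7.2.10 is the endpoint's own section and names the eCRF. The scope is contradictory, so omission is possible but not certain.

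A second defense is that a lost cycle does not vanish from the results. This stands: the reason for each cancellation is recorded and tabulated, and cancellation for pen failure belongs to a secondary endpoint in its own right. The gap concerns the malfunction record and its details.

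A reader might also add malfunctions where the faulty pen was kept in use. The Protocol does not plan for that; 5.4 and 7.2.10 both direct replacement. Nor is it established that affected doses would go unnoticed. The daily dose is recorded in the diary (Protocol 7.1.19), returned pens are reconciled (Protocol 5.6), and overdoses and medication errors with the trial product are tracked in the eCRF (Protocol 8.5.2).

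**Conclusion.** The point holds as a contradiction in reporting scope. Followed as written, 7.2.10 can leave a malfunction that ends in cancellation without a new pen out of the SAP 10.11 table, while the same event appears as a cancellation reason under SAP 10.7. This is a faulty stated rule and not merely missing detail.

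The size is unknown. A reader might infer that the malfunction rate is biased low by some definite fraction, but the documents give no rate and do not show that any such event is expected. The conclusion assumes that sites or the eCRF may have followed 7.2.10 over 5.4; the eCRF pages are not among the documents, so this cannot be checked. The effect is confined to one descriptive secondary safety endpoint. The primary analysis and the formal test of live birth are untouched, and the priority is low.

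**What to change.** - In Protocol 7.2.10, delete the condition that the malfunction must lead to a replaced pen, so that the section has the same scope as 5.4.
- Before database lock, check that every cancellation attributed to pen malfunction in SAP 10.7 has a malfunction record counted in SAP 10.11, and query any gap.
- Reconcile 5.4 and 7.2.10, which direct replacement and continued treatment, with 6.1.5, which allows cancellation. No view is taken here on which clinical rule is right.

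In this trial the second step does the practical work. SAP 9.3.2 dates the last randomization to 17 September 2019. Stimulation begins at randomization and lasts at most 20 days, so pen use ended by early October 2019, before the SAP additions made with Amendment 01 of 19 March 2020. New wording cannot change what sites were told at the time, but the check can still recover missing records.

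The cost is one deleted phrase and one cross-check of two tables. The reported malfunction count may rise slightly.

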ATC Anatomical Therapeutic Chemical Classification System

AUC area under the time-concentration curve

BID "bis in die", two times daily

BMI body mass index

CHO Chinese hamster ovary

CRO contract research organization

DHEA dehydroepiandrosterone

eCRF electronic case report form

ESTHER Evidence-based Stimulation Trial with Human rFSH in Europe and Rest of World

EU European Union

FDA Food and Drug Administration, USA

FSH follicle-stimulating hormone

GCP Good Clinical Practice

GnRH gonadotropin-releasing hormone

GMP Good Manufacturing Practice

C_{max} maximum concentration observed

hCG human chorionic gonadotropin

HLT high level term

ICH International Conference on Harmonisation

ICSI intracytoplasmic sperm injection

ID identifier

Ig immunoglobulin

IM intramuscular

IMP investigational medicinal product

IND investigational new drug (application)

Follitropin Delta, FE 999049 Solution for Injection Clinical Trial Protocol Trial Code: 000002

Date: 25 Apr 2018 E-Study Protocol-22377; Ver. 1.0 Supersedes: None

Page 26 of 159

IRB institutional review board

ITT intention-to-treat

IU international unit

IVF in vitro fertilization

LH luteinizing hormone

LPLV last patient last visit

MedDRA Medical Dictionary for Regulatory Activities

mITT modified intention-to-treat

NCU neonatal care unit

NICU neonatal intensive care unit

NIMP non-investigational medicinal product

NME new molecular entity

OHSS ovarian hyperstimulation syndrome

PCU pediatric care unit

PGD preimplantation genetic diagnosis
PGS preimplantation genetic screening

PP per-protocol PT preferred term

rFSH recombinant follicle-stimulating hormone

RITA Recombinant FSH Investigation in the Treatment of Infertility with ART

SAE serious adverse event

SC subcutaneous

SD standard deviation

SMQ Standardised MedDRA Queries

SUSAR suspected unexpected serious adverse reaction

TID "ter in die", three times daily
TSH thyroid-stimulating hormone

U.S. United States

WHO World Health Organization

Supersedes: None Page 27 of 159

1 INTRODUCTION

1.1 Background

FE 999049 is a human recombinant follicle-stimulating hormone (rFSH) belonging to the pharmaceutical class of gonadotropins. The current trial is intended to support the following indication being pursued for FE 999049 in the United States (U.S.): "Development of multiple follicles and pregnancy after fresh and/or cryopreserved embryo transfer in ovulatory women undergoing assisted reproductive technology (ART)".

FE 999049 is expressed from a host cell line of human fetal retinal origin (PER.C6[®]). The PER.C6[®] cell line is well-characterized, and bio-testing of the master cell bank has demonstrated safety and consistency. FE 999049 is a glycoprotein which is composed of two non-covalently bound polypeptide chains, denoted alfa (α) and beta (β). The α -subunit contains 92 amino acid residues with 5 intrachain-disulphide bonds. The β -subunit contains 111 amino acid residues with 6 intrachain-disulphide bonds. Each subunit is N-glycosylated at two positions, and about 40% of the total mass is carbohydrates.

Ferring received marketing authorization approval for FE 999049 for the indication "Controlled ovarian stimulation for the development of multiple follicles in women undergoing assisted reproductive technologies (ART) such as an in vitro fertilisation (IVF) or intracytoplasmic sperm injection (ICSI) cycle" from the European Commission in 2016. As of early 2018, FE 999049 is approved in 37 countries also including countries outside the European Union (EU) such as Australia, Switzerland, and Canada.

There are no commercially available rFSH products derived from human cell lines in the U.S. The rFSH products currently approved in the U.S. for controlled ovarian stimulation in ovulatory women undergoing ART, e.g. follitropin alfa (GONAL-F, EMD Serono) and follitropin beta (FOLLISTIM, Merck), are derived from a Chinese hamster ovary (CHO) cell line. The amino acid sequence of FE 999049 is identical to the endogenous human FSH sequence and to that in existing CHO-derived rFSH products. Manufacturing from different cell systems leads to glycosylation heterogeneity between rFSH preparations. The glycosylation profile of recombinant proteins is dependent on the expressing cell line and the cell culture conditions. Differences in glycosylation profile, sialic acid pattern and isoform profile have been documented between FE 999049 and existing rFSH products from a CHO cell line. Comparison between the FE 999049 and the GONAL-F and FOLLISTIM profiles indicate differences in acidity and carbohydrate side chains. As CHO cells lack enzymatic functions to construct more complex carbohydrate structures found in humans, the glycosylation profile of FE 999049 is more complex. In addition, FE 999049 contains both $\alpha 2,3$ and $\alpha 2,6$ sialylation patterns, while CHO-derived rFSH products exclusively carry 2,3 linked sialic acid; this difference further contributes to the observed differences in glycosylation profiles between FE 999049 and CHOderived rFSH products. For the purpose of clinical trials, FE 999049 is being treated as a new molecular entity (NME) by the Food and Drug Administration (FDA).

Follitropin Delta, FE 999049 Solution for Injection Clinical Trial Protocol Trial Code: 000002 Date: 25 Apr 2018 E-Study Protocol-22377; Ver. 1.0

> Supersedes: None Page 28 of 159

In total, eight previous clinical trials have been completed as part of the development program for FE 999049, covering four phase 1 trials, two phase 2 trials (one conducted in EU and one in Japan) and two phase 3 trials. A total of 1,927 subjects were included in these trials, of whom 1,112 subjects were exposed to FE 999049, in a range from a single dose up to exposure in three consecutive stimulation cycles. During the phase 3 trials, 665 IVF/ICSI patients were treated with FE 999049 in 1,012 treatment cycles. In addition, two phase 3 trials are currently ongoing; one in Japan and one in Pan-Asia.

The two completed phase 3 trials support the efficacy and safety of FE 999049 (ESTHER-1 / ESTHER-2: Evidence-based Stimulation Trial with Human rFSH in Europe and Rest of World). ESTHER-1 (Trial 000004)¹ was a randomized, controlled, assessor-blind trial conducted in 11 countries in women 18-40 years undergoing IVF/ICSI followed predominantly by single blastocyst transfer. The trial was designed to demonstrate non-inferiority of FE 999049 versus an approved recombinant FSH preparation (GONAL-F) with ongoing pregnancy rate and ongoing implantation rate as co-primary endpoints and also to prospectively evaluate the outcome of an individualized FE 999049 dosing regimen based on the serum anti-Müllerian hormone (AMH) concentration (measured by Elecsys® AMH Immunoassay, Roche Diagnostics) and body weight. The ESTHER-1 trial demonstrated non-inferiority of FE 999049 to GONAL-F for ongoing pregnancy rate and ongoing implantation rate for both the per-protocol (PP) and modified intention-to-treat (mITT; randomized and exposed) populations. For the overall trial population randomized and exposed to FE 999049, the ongoing pregnancy rate was 30.7% and the ongoing implantation rate was 35.2%. Among the women aged ≥35 years, the ongoing pregnancy rate with FE 999049 was 26.9% and the ongoing implantation rate was 30.9%. ESTHER-2 (Trial 000071)² was a safety immunogenicity trial covering up to two repeated treatment cycles in subjects who did not achieve an ongoing pregnancy in ESTHER-1. The trial confirmed the low immunogenicity potential with incidences of anti-FSH antibodies after exposure to FE 999049 of 0.8% in cycle 2 and 1.1% in cycle 3, which was not higher than the incidence of 1.1% in cycle 1 (ESTHER-1) or the incidence of pre-existing anti-FSH antibodies before exposure to FE 999049, which was 1.4%. ESTHER-2 furthermore documented the efficacy of FE 999049 in repeated cycles with similar ongoing pregnancy rates between FE 999049 and GONAL-F as well as documented the safety of FE 999049 in an extended dose range up to 24 µg daily. Cryopreserved cycles using blastocysts derived from the controlled ovarian stimulation cycle in ESTHER-1 or ESTHER-2 and initiated within 1 year after start of stimulation in the subject's last stimulation cycle were followed and showed good efficacy of FE 999049 in cryopreserved cycles with an ongoing pregnancy rate of 32.3% per initiated cycle.

For further information regarding FE 999049, please refer to the current edition of the Investigator's Brochure.³

> Supersedes: None Page 29 of 159

1.2 Scientific Justification for Conducting the Trial

A clinical development program for FE 999049 has been conducted outside the U.S. applying an individualized dosing regimen based on the patient's serum AMH concentration and body weight, and with a fixed dose throughout stimulation. As per FDA recommendations, the FE 999049 dosing regimen in phase 3 in the U.S. will not be based on AMH and body weight. Consequently, a phase 3 program is required for the U.S. to document the efficacy and safety of FE 999049 in the dosing regimen applied in the present trial (see section 3.5.4). The present phase 3 trial will be conducted in the U.S. and will meet the FDA requirements of exposure in the intended target population in the U.S.

The trial is designed to demonstrate the efficacy and safety of FE 999049 in women aged 35-42 years undergoing controlled ovarian stimulation for the development of multiple follicles and pregnancy after fresh and/or cryopreserved cycles.

Cryopreservation of surplus embryos for potential use after the fresh cycle is standard practice in ART treatment, and serves to improve chances of pregnancy from a single stimulation cycle. The development of the vitrification method for freezing of embryos has resulted in significant improvement in post-thaw embryo survival^{4,5} with resulting ongoing pregnancy rates at least as good as those from fresh embryo transfer.^{6,7} As a consequence, the percentage of transfer cycles involving cryopreserved embryos has steadily increased in the U.S. over the last years, with a doubling from 26.6% in 2011 to 52.4% in 2015.^{8,9} The higher frequency of cryopreserved cycles also reflects an increase of "cryo-all" cycles (ovarian stimulation cycles with cryopreservation of all embryos), which when coupled to a gonadotropin-releasing hormone (GnRH) agonist trigger improves patient safety, by reducing the risk of early severe ovarian hyperstimulation syndrome (OHSS).¹⁰ With the observed higher proportion of cryopreserved cycles, it becomes increasingly relevant to include these cycles in the assessment of pregnancy outcome following controlled ovarian stimulation. The present trial is the first U.S. clinical registration trial with a cumulative endpoint covering outcomes from both the fresh and subsequent cryopreserved cycles and thus capturing the clinical efficacy of a single controlled ovarian stimulation cycle in a more complete manner.

The primary endpoint of cumulative ongoing pregnancy rate will be based on the fresh cycle and cryopreserved cycles initiated within 12 months of the start of controlled ovarian stimulation. The cumulative nature of the primary endpoint selected for this trial reflects the evolution in clinical management of infertility. Contemporary approaches have also been applied to improve the safety of infertility treatment, with implementation of GnRH agonist triggering in patients with excessive response to reduce the risk of OHSS as well as implementation of a restrictive transfer policy guided by blastocyst quality and limited to no more than double blastocyst transfer to minimize the incidence of multiple gestation, thereby addressing the most common safety concerns.

Date: 25 Apr 2018 E-Study Protocol-22377; Ver. 1.0 Supersedes: None Page 30 of 159

